**LIST OF ABBREVIATIONS**

Abbreviation/Acronym	Term
AE	Adverse Event
ANOVA	Analysis of Variance
BSCVA	Best Spectacle-Corrected Visual Acuity
CFR	Code of Federal Regulations
CRF/e-CRF	Case Report Form / Electronic Case Report Form
D	Diopter
DOB	Date of Birth
EC	Ethics Committee
FDA	United States Food and Drug Administration
GCPs	Good Clinical Practices
HIPAA	Health Insurance Portability and Accountability Act
ICF	Informed Consent Form
ICH	International Conference on Harmonisation
ID	Identification
IRB	Institutional Review Board
ISO	International Organization for Standardization
logMAR	Logarithm of the Minimum Angle of Resolution
US	United States
USC	United States Code
VA	Visual Acuity

**NOTE:** *The first occurrence of some abbreviations is not spelled out in the document (e.g., units of measure).*

## **1.0 INTRODUCTION**

The aim of this study is to compare the performance of currently marketed Johnson & Johnson Acuvue Vita (senofilcon C) soft contact lenses to the currently marketed Bausch + Lomb Ultra (samfilcon A) soft contact lenses among adapted wearers of Acuvue Oasys soft contact lenses.

## **2.0 OBJECTIVE**

The objective of the study is to evaluate the product performance of currently marketed Acuvue Vita contact lenses (Test) compared to currently marketed Ultra contact lenses (Control).

## **3.1 STUDY DESIGN**

### **3.2 Description of Study Design**

In this randomized, bilateral, double-masked, 1-month study with two parallel groups, approximately 260 subjects (520 eyes) will be enrolled at approximately 10 investigative sites in the United States (US).

Approximately one-half of the subjects (130) will be randomized to receive Test contact lenses and the other half (130) will be randomized to receive Control contact lenses in a 1:1 ratio at the Dispensing Visit. All subjects will be dispensed study lenses according to a unique randomization schedule provided to each site. Both groups will wear the study lenses on a daily wear basis. After two weeks of wearing the study lenses, the subjects will return for an exam, and then continue wearing the same study lenses for the remaining 2 weeks.

Each subject will be required to complete four Take Home Lens Performance Surveys. All take home surveys are required to be completed after a minimum of 5 days of experience with the dispensed study lenses. The first two take home surveys must be returned at the 2-Week Follow-up Visit. The remaining two take home surveys are required to be completed during each of the remaining two weeks (one per week) and must be returned at the final 1-Month Follow-up Visit. All take home surveys will be reviewed by the Investigator for completeness when returned.

Subjects will be required to clean and disinfect their lenses each day using Biotrue™ multi-purpose solution and the contact lens cases provided. The lenses will be worn on a daily wear basis for the entire 1-month study with no scheduled replacement.

### **3.3 Selection of Study Population**

Written informed consent, enrollment in the study, or dispensing of study products cannot begin until the Investigator has received Institutional Review Board (IRB)/Ethics Committee (EC) approval to conduct the study. After receiving IRB approval, recruitment for the study may start at any point after the Investigator agrees, in writing, to participate in the study. The Sponsor and IRB/EC must approve any advertising or other materials used to recruit subjects prior to use of that advertising or material.

Each subject must meet the requirements of the Pre-Screening Tool provided to each site. Each subject will then be assigned a subject identification (ID) number from the Randomization Schedule. Potential subjects are deemed either “Screen Pass” or “Screen Fail.” “Screen Fail” subjects have not met the study inclusion criteria or have met the exclusion criteria. “Screen Fail” subjects cannot participate in the study. Case report forms (Electronic CRFs) will be completed for “Screen Fail” subjects, and the copy of their signed ICF and any information collected as part of screening (e.g., source documents, etc.) must be kept in their permanent records.

“Screen Pass” subjects have met all of the study inclusion criteria and have not met any of the exclusion criteria. Only “Screen Pass” subjects are eligible to participate in the study. Subjects who meet all inclusion criteria but are found not to be eligible to participate in the study due to lens fitting characteristics at the Screening/Dispensing Visit will be exited as a non-dispensed subject.

Once a subject passes the initial screening criteria they are considered active and must be accounted for at every visit until exited (completed or discontinued) from the study. Refer to Section 3.3.5 for subjects determined to be lost to follow-up.

### **3.3.1 Eligibility**

#### **3.3.1.1 Inclusion Criteria**

1. Subjects must be between the ages of 18 and 40 years old, inclusive, on the date the Informed Consent Form (ICF) is signed and have the capacity to provide voluntary informed consent.
2. Subjects must be able to read, understand and provide written informed consent on the Institutional Review Board (IRB)/Ethics Committee (EC) approved ICF and provide authorization as appropriate for local privacy regulations.
3. Subjects must be willing and able to comply with all treatment and follow-up/study procedures.
4. Subjects must be correctable through spherocylindrical refraction to 32 letters (0.3 logMAR) or better (distance, high contrast) in each eye.
5. Subjects must have clear central corneas and be free of any anterior segment disorders.
6. Subjects must be myopic and require contact lens sphere power correction from -0.50 diopter (D) to -6.00 D (considering vertex distance adjustments in both eyes).
7. Subjects must be habitual wearers of Johnson & Johnson Acuvue Oasys single vision spherical soft contact lenses in each eye.
8. Subjects must use a contact lens care regimen on a routine basis.
9. Subjects must agree to wear their study lenses on a daily wear basis for the duration of the study.

#### **3.3.1.2 Exclusion Criteria**

1. Subjects participating in any drug or device clinical investigation within two weeks prior to entry into this study and/or during the period of study participation
2. Subjects who are women of childbearing potential (those who are not surgically sterilized or postmenopausal) are excluded from participation in the investigation if they meet any one of the following conditions:
  - she is currently pregnant
  - she plans to become pregnant during the study
  - she is breastfeeding

3. Subjects with any systemic disease currently affecting ocular health or which in the Investigator's opinion may have an effect on ocular health during the course of the study.
4. Subjects using any systemic or topical medications that will, in the Investigator's opinion, affect ocular physiology or lens performance.
5. Subjects with an active ocular disease or who are using any ocular medication.
6. Subjects who are not correctable to 32 letters (0.3 logMAR) in each eye with soft spherical contact lenses.
7. Subjects who currently wear monovision or multifocal contact lenses.
8. Subjects with refractive astigmatism of 0.75 D or greater in either eye.
9. Subjects who are current Acuvue Oasys wearers who have previously been unsuccessful in wearing Acuvue Vita and/or Ultra contact lenses.
10. Subjects with anisometropia (spherical equivalent) of greater than 2.00 D.
11. Subjects with any grade 2 or greater finding during the slit lamp examination (refer to Appendix B for methods of clinical evaluation). Subjects with corneal infiltrates, of ANY GRADE, are not eligible.
12. Subjects with any "Present" finding during the slit lamp examination (refer to Appendix B for methods of clinical evaluation) that, in the Investigator's judgment, interferes with contact lens wear.
13. Subjects with any scar or neovascularization within the central 6 mm of the cornea. Subjects with minor peripheral corneal scarring (that does not extend into the central area), that in the Investigator's judgment, does not interfere with contact lens wear, are eligible for this study.
14. Subjects who are aphakic.
15. Subjects who are amblyopic.
16. Subjects who have had any corneal surgery (e.g., refractive surgery).
17. Subjects who meet any of the following criteria:
  - the subject is an employee of the investigative site
  - the subject, or a member of the subject's household, is an employee of a marketing research firm
  - the subject, or a member of the subject's household, is an Ophthalmologist, an Optometrist, an Optician, or an Ophthalmic Assistant/Technician
  - the subject, or a member of the subject's household, is an employee of a manufacturer of contact lenses or contact lens care products (e.g., Alcon, Bausch & Lomb, CooperVision, Johnson & Johnson, etc.)

If a subject meets all the inclusion criteria and does not exhibit any of the exclusion criteria, the subject is eligible for entry into the study. Ineligible subjects MUST NOT be enrolled in this study. Any subject enrolled in the study who later is found to have not met the eligibility criteria at entry will be discontinued.

### **3.3.2 Subject Completion**

The subject has completed the study when the 1-Month Follow-up Visit is concluded. Subjects who require further follow-up will be followed according to the AE or Post-Study Follow-Up Section.

### **3.3.3 Subject Discontinuation**

A subject MAY be discontinued (at the discretion of the Investigator, the Sponsor, and/or the IRB/EC) prior to the final study visit for a variety of reasons, including, but not limited to:

- an AE occurring during the course of the study, which precludes continued treatment or follow-up
- persistent grade 3 or 4 slit lamp findings (must be reported to the Sponsor within 24 hours)
- persistent study related symptoms/complaints
- unacceptable distance lens visual acuity (VA)
- unacceptable lens centration
- unacceptable lens movement

A subject MUST be discontinued prior to the final study visit for any of the following reasons:

- voluntary withdrawal
- death
- Investigator decision that it is not in the best medical interest of the subject to continue participation in the investigation
- ineligible at baseline- does not meet the eligibility criteria in the protocol
- inability to maintain recommended wearing schedule
- lack of motivation
- continued failure to follow subject instructions
- subject missed the 2-Week Follow-up Visit
- lost to follow-up (refer to Section 3.3.5)
- instillation of non-medically indicated solution not specified in the protocol
- other eye is discontinued
- becomes pregnant during the study

Prior to discontinuing a subject, every effort should be made to contact the subject, schedule a final study visit, obtain as much follow-up data as possible, and to retrieve all study materials. Adverse events will be followed as described in Section 6. Subject discontinuations will be documented clearly on the source document and applicable electronic CRF (e-CRF). The Investigator should indicate the PRIMARY (one) reason that the subject was discontinued for each eye. Subjects that are discontinued from the study following randomization will not be replaced.

Exit Visit assessments should be completed for early terminated subjects.

### **3.3.4 Screen Failures**

Subjects failing to meet subject selection criteria during Visit 1 (Screening/Dispensing) are considered screen failures, and the Investigator should indicate the PRIMARY (one) reason for the screen failure in the study database (i.e., eligibility or lens fitting characteristics). Data for those subjects considered screen failures due to fitting characteristics will be collected on the corresponding e-CRF.

### 3.3.5 Lost to Follow-up

Subjects who do not return for scheduled follow-up visits, as defined by the visit window and cannot be contacted, are to be considered lost to follow-up. All attempts to contact the subject should be documented and kept with the subject's source documentation, and the applicable e-CRFs will be completed.

### 3.4 Investigators

The study will be conducted at approximately 10 investigative sites located in the US by Investigators who are determined by Bausch + Lomb to be suitably qualified by training and experience to conduct this study. Principal Investigators will be identified on the Device Investigator Agreement Form.

Each Investigator will enroll approximately 26 subjects, 52 eyes. In the event that selected sites do not meet full enrollment, the Sponsor may decide to increase enrollment as needed at other currently active sites and/or additional site(s) may be added to satisfy the enrollment requirements of the study.

### 3.5 Study Duration

Investigators will have four weeks from the enrollment start date communicated by the Sponsor to conduct the Screening/Dispensing Visit(s).

Subjects will be followed for approximately 1 month (unless discontinued or lost to follow-up) from the Dispensing Visit and must adhere to the following schedule:

Visit	Target	Acceptable Visit Range (from Visit test articles are dispensed)
2-Week Follow-up Visit	14 Days	10-18 Days from Dispensing Visit
1-Month Follow-up Visit	30 Days	26-34 Days from Dispensing Visit

The visit range is based on the date study lenses are dispensed. A visit scheduling table will be provided in the initial study shipment to aid the Investigator in scheduling follow-up visits.

### 4.1 STUDY MATERIALS

Bausch + Lomb will provide all lenses, lens cases, and Biotrue™ multi-purpose solution. All materials will be provided to the site prior to the Dispensing Visit. Refer to Product Replacement Section 4.9 for ordering replacement Test or Control product in the case of loss or damage.

Use of other contact lenses or contact lens care systems is not allowed. However, the use of habitual rewetting drops is allowed.

#### **4.2 Description of Test Article**

The currently marketed Johnson & Johnson Acuvue Vita spherical contact lenses will be dispensed in the standard commercial blister packaging in the following:

- Sphere power: -0.50D to -6.00D.
- Diameter: 14.0 mm
- Base curve: 8.4 mm
- Material: senofilcon C
- Packaging solution: buffered saline solution with methyl ether cellulose

#### **4.3 Description of Comparator Product**

The currently marketed Bausch + Lomb Ultra spherical contact lenses will be dispensed in the standard commercial blister packaging in the following:

- Sphere power: -0.50D to -6.00D.
- Diameter: 14.2 mm
- Base curve: 8.5 mm
- Material: samfilcon A
- Packaging solution: 0.5% poloxamine in borate buffered saline

#### **4.4 Instructions for Use and Administration**

##### **4.4.1 Subject Instructions**

- a) All subjects must be given Subject Instructions for the use of study articles (refer to Appendix C for subject instructions) and for precautions and warnings related to contact lens wear. Subjects must comply with the instructions provided to them. Subject Instructions will be supplied to the Investigator by Bausch + Lomb for distribution to the subject.
- b) The Investigator or other designee must review, with the subject, the Subject Instructions and the precautions and warnings, as appropriate for the study.
- c) Any subject who does not follow instructions to a degree that, in the Sponsor or Investigator's opinion, jeopardizes the subject's well-being or the validity of the study, should be discontinued.

##### **4.4.2 Fitting Guide**

The Fitting Guides for the use of the marketed lenses will be provided with the study supplies.

#### **4.5 Other Materials**

##### **4.5.1 Care System**

Bausch + Lomb Biotrue™ multi-purpose solution will be provided for cleaning, rewetting, disinfecting, and storing lenses. Subjects should refer to the package insert for proper lens care instructions. A lens case will also be provided to the subject.

Subjects will be allowed to use their habitual rewetting drops if needed.

No other care products are allowed to be used during this study.

#### **4.6 Packaging and Labeling**

Both the test and control lenses will be in standard commercial blister pack packaging.

#### **4.7 Accountability**

The Investigator or designee will be responsible for keeping current and accurate records of the amount of study articles received and dispensed, and its disposition. The test articles must be stored under the appropriate conditions in a secure area and are to be dispensed only to subjects enrolled in the study, in accordance with the conditions specified in this protocol. Applicable e-CRFs will be used to track accountability for the test articles and to maintain records of the study articles assigned to each enrolled subject.

At time points throughout the study and/or upon completion of the study, the Sponsor/Sponsor's representative may review the e-CRFs to verify accountability.

Following verification, and as directed by the Sponsor, study articles must be returned to the Sponsor at the address listed on the Personnel and Facilities page, or with the Sponsor's permission, disposed of at the site in an appropriate manner.

#### **4.8 Masking/Unmasking**

Both the Investigator and the subjects will be masked to the study treatment. An unmasked designee at each site will be responsible for dispensing study products to the subjects according to the randomization schedule. The randomization schedule will be produced by the Sponsor statistician not otherwise involved in the study until after the database is locked.

Randomization will be completed by the unmasked designee by providing each subject's treatment assignment after the subject has been assigned a subject number (i.e., randomized). The subjects will be assigned randomization numbers sequentially as they are enrolled. The unmasked designee will open the blister packs by removing the foil out of the subject's sight (subject MUST insert lenses). The unmasked designee is also responsible for maintaining study lens inventory, randomization schedule and the Product Accountability Log in a masked fashion.

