### 5.2.2 Dispensing Visit

**NOTE:** All VA measurements **MUST** be made using a phoropter.

**NOTE:** Ensure all lenses/lens types for the subject have been received prior to the Dispensing Visit.

**NOTE:** The Investigator should allow the lenses to properly settle on the eye for a minimum of 5 minutes.

If the Dispensing Visit is occurring on a separate day from the Screening Visit, perform (a) and (b) below, otherwise if the Dispensing Visit occurs on the same day as the Screening Visit, skip to (c).

- a. Perform a slit lamp examination (remove the lenses if the subject wore lenses to the visit). Record the results and findings in the e-CRF.
- b. Reconfirm subject eligibility. If the subject continues to be eligible, continue the Dispensing Visit. If the subject is determined to be ineligible, they must be discontinued and the reason recorded on the Subject Exit Form.
- c. If the subject is eligible, the unmasked designee will dispense 1 pair of the study lenses according to the unique randomization schedule provided to each site. The subject **MUST** insert the lenses.

**NOTE:** Study lenses should be allowed to equilibrate a minimum of five minutes on the eye.

Record the following into the e-CRF:

- The Investigator or designees will ask and record the subject’s responses to the

Study ROC2-17-014 - Protocol

Lens Performance Survey (100-point scales).

- dispensed lens sphere power, type, and lot number
- distance lens VA
- over-refraction and distance VA
- lens wettability
- lens centration
- lens movement

For each eye, compare the high contrast distance lens VA to the high contrast BSCVA obtained previously in the Screening Visit. If the VA has decreased by 10 letters (0.2 logMAR) or more, explain.

- g. The Investigator must assess if the lens fit and VA is acceptable.

Remind the subjects to complete the first two Take Home Lens Performance surveys after a minimum of 5 days of experience with the study lenses for each week and to return the surveys at their next visit.

- h. Subjects who meet all inclusion criteria but are found not to be eligible to participate in the study due to lens fitting characteristics at the Dispensing Visit will be exited as a non-dispensed subject.
- i. The following e-CRFs should be completed.
- Dispensing Visit

If the subject is discontinued or exited at this visit:

- Subject Exit

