## **7.1 Statistical Methods**

### **7.2 Study Endpoints**

#### Primary Effectiveness Endpoints

- For each question on the take home questionnaire at each of four week-long intervals, the proportion of subjects providing a response in the top 3 boxes.
  - Note that these endpoints are not pass/fail criteria for the study. Rather, these are the most important data that will be evaluated.

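### Foil removal is the only subject-facing masking step, no neutral container is described, and subjects may infer the lens maker if the opened blisters can be told apart

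*Combined protocol and SAP*

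**What the plan says.** Section 3.2 describes the study as double-masked, and Section 4.8 (Masking/Unmasking) states: "Both the Investigator and the subjects will be masked to the study treatment". An unmasked designee at each site dispenses the lenses and keeps the inventory, randomization schedule and accountability log in a masked fashion. For what the subject sees, 4.8 gives one instruction: "The unmasked designee will open the blister packs by removing the foil out of the subject's sight (subject MUST insert lenses".

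The packaging is commercial in both arms. Section 4.6: "Both the test and control lenses will be in standard commercial blister pack packaging". Section 4.2, Test: "The currently marketed Johnson & Johnson Acuvue Vita spherical contact lenses will be dispensed in the standard commercial blister packaging". Section 4.3, Control: "The currently marketed Bausch + Lomb Ultra spherical contact lenses will be dispensed in the standard commercial blister packaging". Section 5.2.2, step c, repeats that the designee dispenses one pair and that the subject must insert it. Lenses can also be replaced at an unscheduled visit (5.2.5.2) or a product-dispensing-only visit (5.2.7); neither section describes a masking step.

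Inclusion criterion 7 fixes the subjects' habitual lens: "Subjects must be habitual wearers of Johnson & Johnson Acuvue Oasys single vision spherical soft contact lenses in each eye".

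The primary endpoint in Section 7.2 is, for each take-home question and week, "the proportion of subjects providing a response in the top 3 boxes". The secondary effectiveness endpoints are comfort items on 100-point scales. Both are the subject's own ratings.

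**The concern.** The foil is removed out of sight, but the plan does not say what the subject then takes the lens from. Since the lenses are dispensed in the makers' blisters and no other container is mentioned, the natural reading is that the subject lifts the lens from the opened blister. That is an inference.

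If the opened trays differ visibly, a subject could infer the maker. Every subject already uses the Test maker's Acuvue Oasys, so such a cue might be familiar in one arm and unfamiliar in the other, and its effect need not cancel between arms. All effectiveness outcomes are self-rated, so an expectation effect could not be separated from a lens effect at analysis.

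The foil instruction also mentions only the subject's sight. The Investigator, who must stay masked, judges fit and visual acuity at the Dispensing Visit and is not named in that step.

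**Working it through.** **1. Steps from packaging to rating**

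| Step | What the plan states | What it leaves open |
|---|---|---|
| Packaging (4.2, 4.3, 4.6) | Commercial blister, both arms | Whether opened trays look alike |
| Opening (4.8) | Designee removes foil out of the subject's sight | Whether the Investigator can see |
| Presentation (4.8, 5.2.2) | Subject inserts the lens | From what container |
| Replacement (5.2.5.2, 5.2.7) | Lens type and lot number recorded | Any masking step |
| First rating (5.2.2) | 100-point survey at the Dispensing Visit, after at least 5 minutes of settling | – |
| Primary ratings (3.2, 5.2.5.1) | Take-home surveys after at least 5 days of wear, four in all | – |

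One pair is dispensed, the same pair is re-inserted at the 2-Week Visit (5.2.3), and no replacement is scheduled (3.2). Barring loss or damage, a subject would see a tray once. The Dispensing Visit survey follows within the same visit; the first primary rating comes days later.

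**2. The plan's own power figure**

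Inputs from Section 7.3: p1 = 0.500, p2 = 0.670, n = 130 per group, two-sided alpha 0.05. With d = p2 − p1 and pbar = (p1 + p2)/2:

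- SE0 = √[2·pbar(1 − pbar)/n] = √[2(0.585)(0.415)/130] = 0.0611
- SE1 = √[p1(1 − p1)/n + p2(1 − p2)/n] = √[(0.2500 + 0.2211)/130] = 0.0602
- Power = Φ[(d − 1.96·SE0)/SE1] + Φ[(−d − 1.96·SE0)/SE1] = Φ(0.834) + Φ(−4.81) = 79.8%

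The stated 80% reproduces.

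**3. Illustration of what a cue could do**

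The documents give no recognition rate and no rating shift, so both are assumed. Suppose there is no true difference, both arms have a top-3 rate of 50%, a share r of Test subjects infer the maker, and their top-3 probability rises by b. The spurious difference is r × b. The formula in step 2 with p1 = 0.50 and p2 = 0.50 + r·b gives:

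| r | b | r × b | Rejection rate, one test |
|---|---|---|---|
| 0 | – | 0 | 5.0% |
| 0.10 | 0.10 | 0.01 | 5.3% |
| 0.10 | 0.20 | 0.02 | 6.2% |
| 0.25 | 0.10 | 0.025 | 6.9% |
| 0.25 | 0.20 | 0.05 | 12.7% |
| 0.50 | 0.20 | 0.10 | 36.7% |

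For the last row, SE0 = 0.0617, SE1 = 0.0614 and Φ[(0.10 − 1.96 × 0.0617)/0.0614] = Φ(−0.341) = 36.7%; the other tail is negligible.

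A shift can also hide a difference. If Control is truly 0.67 and Test 0.50, raising Test by 0.05 leaves 0.67 against 0.55, and power falls from 79.8% to 51.0%.

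These are rates for a single test. Section 7.6 tests the take-home responses by week without multiplicity adjustment, so a systematic shift could touch many tests at once.

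**The case against.** The strongest objection is that the decisive fact is missing. Nothing in the documents shows that the trays differ once the foil is off, or that an Acuvue Vita tray would look familiar to an Acuvue Oasys wearer. Inclusion criterion 7 establishes the habitual lens only. This stands, and it makes the point conditional.

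Three further objections also stand. Exposure is brief and precedes the primary ratings by days. The subject instructions (Appendix C) are not in the reviewed text, so a transfer step may exist there or in site materials. Section 7.2 says that the primary endpoints are not pass/fail criteria, which lowers the consequence of one false-positive test.

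A reader might go further than the text allows in several ways:

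- *The trial is in effect unmasked, or foil removal is its only masking measure.* It is only the sole measure facing the subject. Section 4.8 also has the unmasked designee and masked records.
- *The Investigator is unmasked.* Section 4.8 requires the Investigator to be masked and gives dispensing to someone else. The foil step merely fails to name the Investigator.
- *The results will favour the Test lens.* The illustration uses an upward shift in Test for convenience; recognition could act in either direction.
- *The shifts can be judged against a 17-point difference for which the trial was sized.* Section 7.3 sets 130 per group as the maximum affordable number and offers 0.500 against 0.670 as an example.

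What remains is that the plan gives no assurance that the trays look alike and describes no step that would make the question irrelevant, although the person who could take that step is already at each site.

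**Conclusion.** The point holds as a residual gap in masking, worth closing because closing it is cheap. The text establishes commercial blisters in both arms, one subject-facing masking step, no described transfer at first dispensing or replacement, and self-rated effectiveness outcomes. It does not establish that any subject would recognise the maker; that rests on the assumption that the opened trays are distinguishable.

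The Dispensing Visit 100-point survey is the most exposed. The take-home primary endpoint is less so, with at least 5 days of wear in between. Neither the size nor the direction of a bias can be derived from the documents. The rejection rates of about 5% to 37% illustrate assumed recognition of 10% to 50% and assumed shifts of 10 to 20 points; the top value needs both maxima, in one arm only. No sample-size figure changes.

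**What to change.** In Sections 4.8 and 5.2.2, and in the sections under which a replacement lens may be given (5.2.5.2 and 5.2.7), state that the unmasked designee:

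1. works out of sight of both the subject and the Investigator;
2. moves each lens, with its own packaging solution, into the right or left well of an identical unmarked case, from which the subject inserts it;
3. keeps the blister and foil out of sight until the lot number (5.2.2) and accountability (4.7) are recorded. Discarding them at once could lose that information.

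If a transfer step already exists in site materials, 4.8 need only state it.

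The cost is a sentence or two of text, unmarked cases (the sponsor already supplies lens cases, though the plan does not say whether they are unmarked), and, as an estimate, about a minute of extra lens handling per dispensing. The handling is the same in both arms, but may have a small effect on first-insertion comfort. The step does not guarantee masking: the lenses differ in diameter (14.0 against 14.2 mm), base curve (8.4 against 8.5 mm) and material, which an adapted wearer might notice.
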